NIHR CSP	National Institute for Health Research Co-ordinated System for Gaining NHS Permission. This system defines and carries out checks that only need to be done once, and those that are required for each NHS location/organisation.				
Patient	A patient under care who may be eligible for the trial but has not yet consented to participate in any trial related activities.				
Participant	An individual who has given written informed consent and is participating in trial related activities.				

ClinicalTrials.gov.: NCT01972451 Page **9** of **42**

PI	Principal Investigator				
PIS	Participant Information Sheet				
R&D	Research and Development				
RCT	Randomised controlled trial				
REC	Research Ethics Committee				
SAE	Serious Adverse Event				
SAR	Serious Adverse Reaction				
SOP	Standard Operating Procedure				
Sponsor	The primary organisation that oversees and is legally responsible for the clinical trial.				
SSA	Site-Specific Assessment				
SSP	Specialist Screening Practitioner				
SUSAR	Suspected Unexpected Serious Adverse Reaction				
TMF	Trial Master File				
TMG	Trial Management Group				
TSC	Trial Steering Committee				
TSF	Trial Site File				
UKCRC	United Kingdom Clinical Research Collaboration				
WCTU	Wales Cancer Trials Unit				

ClinicalTrials.gov.: NCT01972451 Page **10** of **42**

1.0 Trial schema

ClinicalTrials.gov.: NCT01972451 Page **11** of **42**

2.0 Trial synopsis

Study title:	Feasibility of reduction in Right Sided Bowel cancer through					
Study acronym:	Contrast enhanced Colonoscopy CONSCOP					
Short title:	A feasibility randomised controlled trial (RCT) of contrast enhanced vs non-enhanced colonoscopy in index bowel					
	cancer screening to reduce bowel cancer mortality					
ClinicalTrials.gov No:	NCT01972451					
Funder:	NISCHR	Funder's No:	RfPPB –1021			
Chief Investigator:	[name]					
Sponsor:	Cardiff University	Sponsor No:	SPON 1325-14			
Study period:	2 years	Phase: Feasibility	Feasibility	Number of arms:	2	
Number of participants:	1320	I	I	I		
Investigational Medicinal Products(s) (IMP)	None					

Objectives

- 1. To assess whether enough participants can be recruited into the study (uptake by both participants and screeners) to suggest that it is feasible to run a future, larger scale trial investigating the impact of enhanced colonoscopy on polyp detection and rate of interval cancer detection on follow up.
- 2. To assess whether the enhanced colonoscopy takes an acceptable length of additional time to conduct
- 3. To estimate the proximal serrated polyp detection rate in the intervention arm to inform the sample size calculation of a future trial by allowing an assessment of the possible magnitude of improvement in cancer detection
- 4. To estimate the proportion of samples that are able to be collected as per protocol to inform the design of the translational element of the future trial
- 5. To assess the feasibility of incorporating an economic evaluation into a larger scale trial by exploring issues relating to collection of data on resource utilization, costs and outcome measures.

Main inclusion criteria:

- 1. All participants testing positive on Faecal Occult Blood Test (FOBT) in the screening program who are eligible and appropriate for an index screening colonoscopy will be offered participation in the study.
- 2. Written informed consent

ClinicalTrials.gov.: NCT01972451 Page **12** of **42**

See Section 6.1 for full inclusion criteria.

Main exclusion criteria:

- 1. Any participants not deemed fit for colonoscopy on the screening program or undergoing alternative investigation such as CT Pneumocolon or minimal prep CT scan as their index procedure instead.
- 2. Participants who have undergone previous colorectal surgery will be excluded from the study though their standard management in the screening program will continue unchanged.
- 3. Anyone with a known allergy to a food colouring agent.
- 4. Previous inclusion in the trial

See Section 6.2 for full exclusion criteria.

Interventions:

Arm A: Colonoscopy without enhanced dye

Arm B: Colonoscopy with enhanced dye

Trial assessments:

At colonoscopy data will be collected on the procedure logistics (time, completion, resource utilisation), associated adverse events, results and patient comfort (see section 9).

Additionally, after local reporting, all proximal colonic polyps (i.e. above the splenic flexure) should be sent for central analysis (see section 13)

Endpoints:

- Proportion of screening service providers who agree to participate in the trial
- Proportion of eligible patients who give consent.
- Procedure time
- Colonoscopy completion rate
- Proximal serrated polyps detection rate
- Proportion of proximal polyp samples that are able to be collected as per protocol
- Resource utilisation: staff time, consumables used during the procedures, use of sedation and other agents to improve patient comfort.
- Adverse events
- Patient comfort scores

ClinicalTrials.gov.: NCT01972451 Page **13** of **42**

2.1 Lay summary

Colorectal cancer is the second leading cause of cancer deaths in the UK (1). The Bowel Cancer Screening Programme (BCSP) was implemented to reduce deaths by the early prevention and detection of bowel cancer. Results from the first few years of screening and previous smaller studies show that while in its current form it will save many lives, there continue to be polyps and cancers in the right side of the colon that may be difficult to detect. There is some evidence that these types of polyps (serrated polyps) may be at least partly responsible for cancers missed at the initial colonoscopy and have a faster rate of growth to cancer compared to conventional polyps (adenomas).

We propose to examine participants undergoing screening colonoscopy with the addition of a contrast dye (a safe food colouring agent base already used in various bowel camera procedures in standard clinical practice). This has been shown to improve detection of conventional polyps significantly (2) and only takes a few more minutes of extra time. The study is a randomised controlled feasibility study comparing two groups, with and without use of dye spray throughout the right colon. Our primary aim is to study the feasibility of undertaking these procedures (i.e. assessment of acceptability by participants and colonoscopists, including time and costs involved in undertaking the enhanced approach). In addition to this we will also be assessing whether this technique helps to improve the detection rates of right-sided polyps in order to inform the sample size for a larger study. Removal of these polyps will enable further laboratory analysis of a collection of polyp samples in order to assess if such a sample collection might be able to answer the question of biological behaviour and growth pattern to cancer in a larger subsequent study within the BCSP. This will help to inform further studies to assess the impact of improved detection and potentially reduced incidence of interval or missed bowel cancers in longer term follow up.

We aim to recruit 1320 participants (660 per group) over a 12-month period involving all participating bowel cancer screening centres in Wales. All eligible participants (eligibility confirmed by SSP) undertaking the BCSP will be invited to the study and participant randomisation will be performed centrally. The data collected by the BCSP nurse will include all the performance parameters already undertaken as part of the BCSP.

ClinicalTrials.gov.: NCT01972451 Page **14** of **42**

3.0 Background, rationale and objectives

Background

Bowel cancer screening started in 2006 in the UK subsequent to evidence from large-scale randomized trials on stool based faecal occult blood testing followed by colonoscopy for those individuals testing positive (3-6). This strategy has clearly been proven to reduce mortality from bowel cancer by 15% (6). Although colonoscopic prevention of colorectal cancer (CRC) through removal of pre-malignant polyps and earlier detection of cancer has proven to be generally safe as well as effective, its effectiveness seems to be variable and somewhat limited in the proximal colon (7, 8). Some studies have cast doubt over the effectiveness of colonoscopy at reducing the incidence and mortality of proximal bowel cancer (7, 9), as relatively high incidence rates of these cancers are found after colonoscopy, referred to as interval cancers (10). Reported incidence rates of interval cancers vary greatly, ranging from 1 in 130 to 1 in 1,000 colonoscopies, or 1 out of 13 to 1 out 45 of all diagnosed CRCs (8, 11).

The incidence of these interval cancers is therefore significant and it may also falsely reassure screened individuals. Two types of factors may contribute to the occurrence of interval CRCs, namely technical, endoscopist dependent factors possibly due to the quality of the procedure and biology dependent factors i.e. potentially due to different morphology and rate of growth of these right-sided polyps (12, 13). Overall, the exact contribution of each of these factors remains largely unknown though it would seem logical to minimize any operator or procedure dependent factors in order to achieve the best outcome and yield from colonoscopy.

Current evidence on right side or proximal colonic polyps found at colonoscopy is mostly based on relatively small retrospective studies partly responsible for the variation in incidence of these. Some studies have suggested that these right-sided polyps are more likely to be "Flat" or non-polypoid in morphology thus making them more difficult to detect (14, 15). Other studies have suggested that right sided polyps are more likely to be serrated polyps as compared to those in the left or distal colon and that they follow an accelerated different pathway to colorectal cancer as compared to the conventional adenomas following the traditional adenoma carcinoma sequence (16). The current available evidence on serrated polyps in the right colon, their natural history, pathways of progression to colorectal cancer and difficulties with detection are all based on relatively small retrospective studies with wide variation in incidence and prevalence of these (17). They are thought to account for a significant proportion of missed or interval colorectal cancers (18). Unlike conventional colonic adenoma surveillance, the appropriate surveillance interval for these serrated polyps is uncertain due to the paucity of accurate data on their detection rates and contribution to cancer and are again based on small retrospective studies and consensus recommendations with a relatively low evidence base (10, 17).

The technique of contrast enhanced colonoscopy with the use of dye spray has been investigated in numerous studies in different settings and in almost all studies has been demonstrated to increase polyp detection rates (19-23). In contrast, newer methods of digital contrast enhancement though very promising and of help in morphological characterization of polyps and cancers have failed to conclusively demonstrate a significant increase in polyp detection rates when controlled for other variables (24). Digital contrast enhancement technology also varies between commercial products for colonoscopy unlike the dye spray technique that is universally applicable. A Cochrane review on the topic of contrast enhanced colonoscopy has also analysed studies using the dye spray technique though not in the setting of screening and found a positive correlation between polyps detected and use of the technique (21). Pan colonic dye spray during colonoscopy already forms part of standard

ClinicalTrials.gov.: NCT01972451 Page **15** of **42**

practice in other settings such as colonoscopic surveillance for neoplasia detection in high risk cases of inflammatory bowel disease and is part of national guidelines (25) in that setting.

Various studies have demonstrated that there are a number of variables that potentially affect adenoma, polyp and cancer detection rates such as quality of bowel preparation, training and experience of the Colonoscopist, various factors related to technique as well as others including those mentioned above. The bowel cancer-screening program provides the appropriate setting to therefore investigate the research question with the best current standardization of these variables. Colonoscopists in England & Wales have to undergo a rigorous assessment and accreditation process in order to achieve a high quality minimum standard and minimum standard criteria such as adenoma detection rates, withdrawal times etc. that are monitored (26). Patient related outcomes including comfort scores, lesions detected and plans and outcomes of management of these are also strictly monitored. It would therefore seem logical to integrate this very clinical and patient focused research question with the health service as it potentially provides an accurate assessment of impact as well as route to improve the service provided to screened individuals and possible reduction in the incidence of interval cancers. The outcomes would still be applicable to colonoscopy even outside the setting of screening and would thus have a wider impact. It is therefore important particularly in the context of the screening program to assess the feasibility of this change in colonoscopic technique through dye spray being acceptable in the first instance to participants, colonoscopists and the program and NHS.

Prior to committing resource to any intervention to potentially reduce interval cancers it seems sensible to analyse and justify the clinical and cost effectiveness of the approach if appropriate. If the intervention is deemed feasible (and we outline the specific criteria for this in the application) then a larger longer-term study would be justified to answer the question of outcomes with regard to interval cancer detection and also appropriate surveillance for serrated polyps that do not follow the same pathway to cancer as conventional adenomas. This study aims to test the feasibility of undertaking such an intervention within the setting of the BCSP in Wales in order to inform the above.

Research Question

Is it feasible and acceptable to participants, professionals and the screening program to undertake an enhanced colonoscopy technique during screening and is the time taken and resource needed for this likely to be considered feasible and acceptable by organisations in charge of screening?

Specific Objectives

- 1. To assess whether enough patients can be recruited into the study to suggest that it is feasible to run a future, larger scale trial investigating the impact of enhanced colonoscopy on cancer detection
- 2. To assess whether the enhanced colonoscopy takes an acceptable length of additional time to conduct
- 3. To estimate the proximal serrated polyp detection rate in the intervention arm to inform the sample size calculation of the future trial by allowing assessment of the possible magnitude of improvement in cancer detection
- 4. To estimate the proportion of samples that are able to be collected as per protocol to inform the design of the translational element of the future trial
- 5. To assess the feasibility of incorporating an economic evaluation into a larger scale trial by exploring issues relating to collection of data relating to resource utilization, costs and outcome measures.

ClinicalTrials.gov.: NCT01972451 Page **16** of **42**

4.0 Study design

A feasibility randomised open controlled trial (RCT) of contrast enhanced vs non-enhanced colonscopy in index bowel cancer screening to reduce bowel cancer mortality. The data obtained in this study will enable the assessment of the feasibility and design of a future RCT that will be powered to look for a reduction in bowel cancer mortality.

4.1 Risk assessment

A Trial Risk Assessment has been completed by the WCTU to identify the potential hazards associated with the trial and to assess the likelihood of those hazards occurring and resulting in harm. This risk assessment includes:

- The risk to participant safety in relation to the intervention
- All other risks related to the design and methods of the trial (including risks to participant safety and rights as well as data integrity)

The potential risks have been balanced against the level of risk that a trial participant would be exposed to outside of the trial. This trial has been categorised as a low risk trial where the level of risk is no higher than the risk of standard medical care. A copy of the trial risk assessment may be requested from the WCTU Trial Manager. The trial risk assessment is used to determine the intensity and focus of monitoring activity (see section 11).

ClinicalTrials.gov.: NCT01972451 Page **17** of **42**

5.0 Participating site selection

All bowel screening units in the Bowel Screening Wales screening programme will be invited to participate in this study. All sites who are interested in participating in the trial will be required to complete a registration form to confirm that they have adequate resources and experience to conduct the trial.

The following documentation must be completed and received by the WCTU in order for a site to begin recruitment:

- Confirmation of local R&D approval
- Signed partnership agreement between the host care organisation and Sponsor
- All site SSPs and colonoscopists must have attended site initiation training
- A copy of the most recent approved version of the Participant Information Sheet(s) and Consent Form(s) on host care organisation headed paper
- Completed Delegation Log (signature list and delegation of responsibilities)
- Full contact details for all host care organisation personnel involved, indicating preferred contact

Once all the documentation has been received at the WCTU, confirmation of site approval will be sent by the WCTU to the site PI.

All documentation must be stored in the Investigator Site File (ISF) at the site and in the Trial Site File (TSF) at the WCTU. The WCTU must be notified of any changes to the trial personnel and their responsibilities during the running of the trial and the respective trial files must contain this up-to-date information.

Occasionally during the trial, amendments may be made to the trial documentation listed above. WCTU will issue the site with the latest version of the documents as soon as they become available. It is the responsibility of the site to ensure that they obtain local R&D approval for the new documents, and that all relevant staff, are working to the current versions once R&D approval has been obtained.

Site initiation will be by attendance at a national CONSCOP launch meeting, or by teleconference or site visit if attendance of key personnel is unfeasible.

ClinicalTrials.gov.: NCT01972451 Page **18** of **42**

6.0 Participant eligibility

Any queries about whether a patient is eligible to enter the trial should be discussed with the WCTU **before** randomisation. Any issues will then be raised with the CI or one of the clinical Co-Investigators in the CI's absence.

Patients are eligible for the trial if all the inclusion criteria (Section 6.1) are met and none of the exclusion criteria (Section 6.2) apply.

The SSP should identify eligible patients prior to ringing patients to conduct the Telephone Assessment Clinic to discuss their colonoscopy.

6.1 Inclusion criteria

Patients meeting the following criteria may be included in the trial:

- 1. All participants testing positive on Faecal Occult Blood Test (FOBT) in the screening program who are eligible and appropriate for an index screening colonoscopy will be offered participation in the study.
- 2. The patient has provided written informed consent.

6.2 Exclusion criteria

If any of the following criteria apply, patients cannot be included in the trial:

- Any participants not deemed fit for colonoscopy on the screening program or undergoing alternative investigation such as CT pneumocolon or minimal prep CT scan as their index procedure instead.
- 2. Participants who have undergone previous colorectal surgery will be excluded from the study though their standard management in the screening program will continue unchanged.
- 3. Anyone with a known allergy to a food colouring agent.
- 4. Previous inclusion in the trial

6.3 Informed consent

During the Telephone Assessment Clinic, the SSP should describe the study to the patient. A full explanation should be given of the investigative options, including the conventional and generally accepted methods of investigation. All patients must be informed of the aims of the study, the possible adverse events, the procedures and possible hazards to which they may be exposed. They will be informed of the strict confidentiality of their patient data, but that their medical records may be reviewed for trial purposes by authorised individuals other than their treating physician. The SSP should tell the patient that they will be sent more information about the study (the CONSCOP Patient Information Sheet (PIS)) through the post along with two consent forms:

- the standard colonoscopy consent form
- and the CONSCOP informed consent form.

ClinicalTrials.gov.: NCT01972451 Page **19** of **42**

The patient should be asked to bring these to their colonoscopy appointment. A contact number for someone at the site will be on the PIS should the patient wish to discuss any aspect of the trial.

Following the phone call, the SSP should randomise all eligible patients (see section 7). This can be done before informed consent has been obtained.

On the day of the procedure after booking at the reception desk, patients will be taken to the admissions bay as usual. Routine admissions procedures for the patient will be followed. The patient will then be seen by the SSP to confirm that they are happy to participate in the trial and written consent forms will be collected in accordance with the principles of Good Clinical Practice. **The site team must not tell the patient which trial arm they have been allocated to until consent has been obtained.** They should sign just the standard colonoscopy consent form if they do not wish to participate in the trial. If they do wish to participate in the trial then they must sign both consent forms. One copy of the CONSCOP informed consent form should be given to the participant but the original copy should be kept in the investigator site file and a further copy should be kept with participant's hospital notes.

The right of the participant to refuse to participate in the trial without giving reasons at any time must be respected. Similarly, the participant must remain free to withdraw at any time from the protocol without giving reasons and without prejudicing his/her further treatment.

For all randomised patients (including those who have only signed the standard colonoscopy consent form), the following screening information should be returned to WCTU via the CONSCOP screening log

- BSW number
- CONSCOP trial ID
- Whether or not informed consent was obtained
- If not, reason:
 - Withdrew consent after discovering trial arm
 - Not interested in taking part in study
 - Patient ineligible (previous colorectal surgery)
 - Patient ineligible (unfit for colonoscopy)
 - Patient ineligible (allergy)
 - Patient ineligible (not index screening colonoscopy)
 - Patient ineligible (previous inclusion in the trial)
 - o Other

ClinicalTrials.gov.: NCT01972451 Page **20** of **42**

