7.0 Randomisation

This is a randomised controlled trial therefore neither the participants nor their physicians will be able to choose the participant's colonoscopy method. The method will be allocated randomly using a computer-based algorithm. This is to ensure that the groups of participants receiving each of the different methods are similar.

The SSP must confirm the eligibility of a patient in the patient's medical notes prior to randomisation.

Participant randomisation will be performed by the SSP using a central randomisation system.

Within 2 days prior to a colonoscopy list (after sending out the bowel preparation kit to those patients), the SSP should randomise the patients on that list to either an enhanced or non-enhanced colonoscopy. This can be done either by telephone or by the internet:

Telephone (Mon – Fri, 9am-5pm): [name]

Internet (Anytime): http://www.wctu.org.uk/rando

Please consult the additional "CONSCOP Trial Randomisation Service User Guide" document for detailed instructions as to how to do this.

Once randomisation is complete, the SSP should enter the trial number that they are given by the central system onto a label on the patient's notes.

ClinicalTrials.gov.: NCT01972451 Page **21** of **42**

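### Allocation is not concealed from the staff who take consent: patients are randomised to a named arm before the day on which written consent is collected

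*Protocol*

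**What the plan says.** All references are to the Protocol.

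- **Order of events.** Section 6.3: "Following the phone call, the SSP should randomise all eligible patients (see section 7). This can be done before informed consent has been obtained". Section 7.0 fixes the time at no more than 2 days before the list, when "the SSP should randomise the patients on that list to either an enhanced or non-enhanced colonoscopy". Written consent is collected on the day of the procedure: "The patient will then be seen by the SSP to confirm that they are happy to participate in the trial".
- **Concealment.** The only instruction concerns the patient: "The site team must not tell the patient which trial arm they have been allocated to until consent has been obtained".
- **Exit after allocation.** The screening log in section 6.3 covers all randomised patients, including those who sign only the standard colonoscopy form. One of its coded reasons for no consent is "Withdrew consent after discovering trial arm". Section 11.3 counts anyone who withdraws before the colonoscopy as never having consented. Section 9.1 takes case report form (CRF) data from consenters only.
- **Eligibility.** Section 6.0 requires every inclusion criterion to be met. The second criterion in section 6.1 is: "The patient has provided written informed consent". Section 7.0 adds: "The SSP must confirm the eligibility of a patient in the patient's medical notes prior to randomisation".
- **Numbers.** Section 12.2 expects about 2200 eligible patients in a year and a consent proportion that may reach 60%, giving 1320. Objective 2 is a non-inferiority test of procedure time (SD 15 minutes, expected excess 12, margin 15, one-sided alpha 0.05). It must be passed before a full trial is considered.

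**The concern.** Randomisation makes the arms comparable only if entry to the comparison cannot depend on the arm. Here the SSP obtains a named allocation first, and an SSP then has the conversation in which the patient confirms or declines. Even unintended differences in how that conversation goes could make the consenters in one arm differ from those in the other. After signature the patient may learn the arm and withdraw before the procedure, and section 11.3 then removes that patient as a non-consenter.

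The between-arm comparison of procedure time is the most exposed, because it is a go/no-go gate and only 3 minutes separate the expected excess from the margin. The detection rate in the intervention arm (Objective 3) is exposed to a lesser degree, through the mix of patients who remain in that arm. Objective 1 is little affected, because its denominator is all eligible patients.

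**Working it through.** **1. Can the staff taking consent know the arm?** Section 7.0 has the SSP run the randomisation to a named arm. Section 6.3 forbids the site team to tell the patient the arm before consent, an instruction that makes sense only if the team may already know it. No section withholds the arm from the person taking consent. Randomising before consent is worded as a permission. But with consent collected on the day and randomisation done in the 2 days before the list, it is in practice the normal order.

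**2. Can the sections all be followed?** Section 6.0 makes every inclusion criterion part of eligibility, section 6.1 makes written consent one of them, and section 7.0 requires eligibility to be confirmed before randomisation. Together they put consent first, whereas section 6.3 allows randomisation first. The glossary also defines a participant as someone who has given written consent, and section 12.1 speaks of randomising participants.

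**3. The plan's own figure.** 2200 × 0.60 = 1320, as stated. If all eligible patients are randomised, 2200 − 1320 = 880 (40%) leave after allocation through planned non-consent.

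**4. Sensitivity of Objective 2 (hypothetical).** Inputs from section 12.2: SD 15, margin 15, one-sided alpha 0.05, 1320 / 2 = 660 per arm. The shift b, in minutes, is an assumption.

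- SE = 15 × √(2/660) = 0.826 minutes.
- The test passes if the estimated excess is below 15 − 1.645 × 0.826 = 13.64 minutes.
- At a true excess of 15, P(pass) = Φ(−b/0.826 − 1.645). At a true excess of 12, P(pass) = Φ((3 − b)/0.826 − 1.645).

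| Shift b in the dye-arm excess | False pass at true 15 | Power at true 12 |
|---|---|---|
| −1.0 | 33.2% | 99.9% |
| −0.5 | 14.9% | 99.5% |
| 0 | 5.0% | 97.7% |
| +0.5 | 1.2% | 91.7% |
| +1.0 | 0.2% | 78.1% |

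A negative shift means that longer cases are lost from the dye arm; a positive shift means the opposite. Nothing in the document says which would occur.

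**5. How a shift of this order could arise (hypothetical).** Assume consent of 62% in the control arm and 58% in the dye arm. Assume also that 20% of patients take 15 minutes longer than the rest, and that the whole shortfall comes from them. Their share of dye-arm consenters is (0.20 × 0.62 − 0.04)/0.58 = 0.145, so b = 15 × (0.145 − 0.20) = −0.83 minutes.

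**6. Would the log show it?** With about 1100 randomised per arm, a comparison of 62% with 58% has pooled proportion 0.60 and SE √(2 × 0.60 × 0.40/1100) = 0.0209. Power is Φ(0.04/0.0209 − 1.96) = 48% (two-sided 0.05).

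**The case against.** Four points on the other side have force.

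- **The patient decides, and does so unaware of the arm.** The trial is explained at the telephone assessment, before allocation, and the information sheet and forms are posted. A reader might infer that someone who knows the arm decides who enters. The document does not support that: it leaves room for staff influence but gives no evidence of steering. Nor does it say that the same SSP does both steps.
- **Non-consent is not bias.** A reader might take 880 of 2200 as the size of the problem. Refusal unrelated to the arm affects external validity, which section 12.2 already guards with its 50% recruitment threshold. Only arm-related loss biases the comparison.
- **The log is a real safeguard.** It records consent status and reason for every randomised patient, so consent can be compared by arm. Gross selection would usually show. If a tenth of would-be consenters were lost in the dye arm, consent there would fall from 60% to 54%. With pooled proportion 0.57 the SE is √(2 × 0.57 × 0.43/1100) = 0.0211, and power is Φ(0.06/0.0211 − 1.96) = about 81%.
- **The contradiction is partly one of wording.** Section 6.3 openly permits the order, and a clarifying sentence would remove the conflict.

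These points limit the claim but do not remove it. The log can reveal an imbalance in numbers but cannot repair one, and a smaller imbalance can escape it. Equal consent rates can also hide different kinds of patients. Keeping the patient unaware until signature does not prevent arm-driven withdrawal between disclosure and colonoscopy.

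**Conclusion.** The point holds. Allocation is not concealed from the staff taking consent, randomised patients can leave the comparison after allocation, and sections 6.0, 6.1, 6.3 and 7.0 disagree on the order of consent and randomisation. That staff know the arm is a strong inference from sections 6.3 and 7.0, not a stated fact.

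The size and direction of any bias cannot be derived from the document. The rise in the false-pass rate from 5% to about 15% to 33% rests on an assumed shift of 0.5 to 1 minute favouring the dye arm, with 660 per arm and one-sided 0.05. It shows how little selection the 3-minute gap tolerates and is not a prediction. A shift the other way would cost power instead.

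A reader might infer that all the trial's endpoints are compromised. The document does not support that: Objective 2 is the only formal between-arm test, Objective 3 is a single-arm estimate, and no test is stated for comfort scores or adverse events. For a feasibility study this should be fixed, preferably before recruitment, but it does not invalidate the design.

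**What to change.** Amend sections 6.3 and 7.0 in one of two ways:

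1. Record the signed trial consent form first and run the existing online randomisation afterwards, on the day. Section 7.0 already offers the internet route at any time. Planned N stays at 1320, and exclusion after randomisation for non-consent falls from about 880 to about zero.
2. If sites need allocations earlier for list planning, keep the present timing but have the arm held by staff who do not take consent until the form is signed.

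In either case, align sections 6.1, 6.3 and 7.0 on the order of consent and randomisation. Keep the existing log for all eligible patients, so that Objective 1 retains its denominator. Where randomisation has already occurred, report consent, and withdrawal after the arm is disclosed, by arm.

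The cost is a protocol amendment plus one practical burden. Under the first option, the number of longer procedures on a list is known only on the day, which matters when section 8.2 expects 12 to 15 extra minutes on an average of 30. Under the second, existing staff outside the consent process must hold the allocation. The second disturbs list planning less, while the first also removes exclusion for non-consent after randomisation.
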